7.9 Data Management

Prior to initiating this study, a common data model will be prepared along with transfer agreement for Denmark to receive data from Sweden and Norway, including preparation of a clear management plan for data handling to ensure protection of subject privacy. The data management of the variables will be performed before sending the final data to Denmark. Because of legal restrictions, Danish investigators will not be able to transfer the data out of Denmark. Therefore, all data will be received and analyzed by Danish investigators.

All data collected for the study should be recorded accurately, promptly, and legibly. For primary data collection, the investigator or qualified designee is responsible for recording and verifying the accuracy of subject data. For data not obtained from a primary source (i.e., secondary data, such as claims and electronic health records), the investigator is responsible for reviewing data quality and relevance to the best of the investigator's knowledge. By signing this protocol either electronically or written, the investigator confirms that the quality and relevance of data has been assessed to meet the minimum requirements for all study objectives.

If this study has been outsourced, the institutional policies of the supplier should be followed for development of data management plans. However, the supplier should ensure compliance with Good Pharmacoepidemiology Practice, and all applicable federal, state, and local laws, rules and regulations relating to the conduct of the study.

PRODUCT: V501/V503	PROTOCOL/AMENDMENT VERSION NO.: V503-088-01-v1
REVOPS ID NO: NIS009722	CORE DRC APPROVAL DATE: 18JUL2024
EPIDEMIOLOGY NO.(PE STUDIES ONLY): EP08039.017	

Data Management Software and Hardware (per country):

Sweden

- SAS version 9.4 will be used for data management and statistical analyses.
- Stata version 18.0 will be used for statistical analyses.
- R may be used for complimentary statistical analyses and generation of graphs.
- All hardware utilized in the study is procured through central KI purchasing procedures and follow strict regulations on performance and capacity.

Norway

All data management and statistical computing on registry data delivered to the project will be performed in the most recent version of Stata (currently 18.0 MP (StataCorp) or R, using syntax scripts generated by the CRN study team. All syntax that influences the dataset (data management) or generates results (analyses) is stored in the project data script folder on CRN's secure server. Syntax files will be numbered according to the order in which they should be run. All syntax written by one member of the CRN study team is checked by another member of the CRN study team. All output (results) is also assessed by the CRN study team, and any unexpected result is investigated further to double-check that no scripting error has occurred. Tables and figures are transferred to the report template by one member of the CRN study team and the transfer is checked by another member of the CRN study team. All data management, analyses or other data procedures are logged, including information on when the procedure took place and who performed the procedure.

Denmark

A data management plan will be developed to guide and instruct the data manager on the project. This will include a list of the registers used (see section 7.4) and a detailed instruction on the criteria for data extraction from each register. Furthermore, the steps listed in section 7.7 will be part of the data management plan. All steps in data management plan will be gone through between the data manager and investigator before execution and evaluated after execution. The SAS software and the R statistical software will be used in the data management.

Description of Data Preparation and Methods for Data Retrieval and Collection:

Sweden: All data retrieval is documented and traceable through the formal data specification orders exchanged with the registry data holders before data delivery, inclusive of exact variable and format lists. Data collection will take place from Swedish registry data holders through the import of SAS.7bdat format and/or CSV files. Only electronic data will be used, there are no paper-based data in this project. No eCRFs are applicable. Data quality checking will occur right after delivery from the registry data holder, ensuring that requested data are logical and transparent. Data cleaning will be done using SAS version 9.4 and documented through log files and validation procedures as described below. Statistical analyses will be performed using softwares specified above.

PRODUCT: V501/V503	PROTOCOL/AMENDMENT VERSION NO.: V503-088-01-v1
REVOPS ID NO: NIS009722	CORE DRC APPROVAL DATE: 18JUL2024
EPIDEMIOLOGY NO.(PE STUDIES ONLY): EP08039.017	

Denmark: All data collected in this project are electronic data derived from existing registers (section 7.4). Data will be collected according to the specified criteria in the data management plan i.e., specified age intervals, specified diagnoses etc. that will be developed for this protocol. No data collector will be used in this protocol.

Norway: Data collection will take place from Norwegian registry data holders through the import of CSV and/or dta files. Each registry will securely transfer data to the delivery unit at the CRN, including:

- RRP incidence data from the Norwegian Patient Registry (NPR)
- HPV vaccination status from the Norwegian Immunisation Registry (SYSVAK)
- Prescription data from the Norwegian Prescribed Drug Registry
- Sociodemographic data from Statistics Norway
- Norpat codes from the Norwegian Cancer Registry (CRN)
- Population data from the National Population Registry

Only electronic data will be used, there are no paper-based data in this project. Data received from each registry will be documented by a data-in procedure, including quality checks of incoming data and documentation of data reception and links to the application for data, the data file itself and any documentation accompanying the data file. Data-in and its associated forms are stored in the project data documentation folder. General quality checks of incoming data are carried out to ensure that the data delivery coincides with the data application, e.g., that all the expected variables have been included and contain the expected information, and that the correct number of individuals have been included. Checks will be carried out and any errors reported to the delivering registry within 2 weeks of receipt of data. Any new deliveries of data will be documented by the data-in procedure. All raw data received from the registries will be stored on CRN's secure server as they were delivered to the project, with access restricted to project members only. All data and associated files are backed up regularly and automatically. Data cleaning will be done using Stata or R and documented through syntax scripts and validation procedures as described above.

7.10 Programming Quality

Good programming standards should be followed during all programming associated with the study. No error statements should occur when programs are run. Warning statements should be avoided whenever possible. If warning statements do appear, they should be accompanied by explanatory text, stating why they do not represent a program. A Programming Information Document should be drafted that describes:

- the order by which the SAS or other software programs were run;
- a description of the SAS or other software programs;
- the program's name, location, and author;
- the date of creation and modification where applicable;
- the name and location of the SAS or other software datasets input and output; and
- the purpose of the program.

PRODUCT: V501/V503	PROTOCOL/AMENDMENT VERSION NO.: V503-088-01-v1
REVOPS ID NO: NIS009722	CORE DRC APPROVAL DATE: 18JUL2024
EPIDEMIOLOGY NO.(PE STUDIES ONLY): EP08039.017	

Data validation should occur throughout the data management and analysis process. Data quality checks may include, but are not limited to, programming checks by an individual who is not main programmer for the study, internal dataset consistency, consistency between datasets, external checks with other available databases for verification of items such as birthdates and vaccination dates and checks to ensure that protocol and SAP criteria were met. If validation checks were not satisfied, then an examination of the problem should be performed on the dataset or datasets in question and the problem resolved. All data validation, quality checks, and resolution of issues identified should be recorded on a standardized form used for this study.

Institution will retain copies of electronic versions of the analytic datasets and programs, and computer printouts. This includes any relevant computer code that produces the basis of tables, discussions, graphs, or interpretations in the study report.

The procedures are applicable to all study programing, tables and figures associated with study final report, and additional analyses requested by MSD.

7.11 Data Analysis

Data Pooling

Data from the three Nordic countries will be pooled by developing a common data model. The list of variables, including the primary exposure, outcome, and covariates will be defined and a data dictionary will be created. Variable types, names, and formats will be standardized. An indicator variable for the country (Sweden/Norway/Denmark) and unique study IDs will be generated. Datasets from the three countries will be concatenated and checked for consistency and errors, including logic checks.

Primary Objective: Nested Case-Control Study

Conditional logistic regression will be used for estimation of odds ratios (ORs) and corresponding 95% confidence intervals in the pooled analysis using 1-step approach, with adjustment for clustering and adjustment for relevant covariates; all measured with similar high accuracy in each country. Each case subject and her controls constitute a risk stratum, or a risk set matched on age at diagnosis, calendar year, and region where case was diagnosed. The distribution of these factors is therefore equalized in the model by design, which removes the need for adjusting for these factors so long as the risk strata are retained. For controls with longer follow-up than the case to which they are matched, the follow-up will be truncated to match that of the case. Regarding education level and income, it was decided not to match on these factors, as they may be of interest to study as confounders or effect modifiers.

To account for prevalent RRP cases undiagnosed at the time of vaccination, a buffer period of 6 months will be applied in sensitivity analyses, where cases occurring among individuals within this time period (from last vaccination dose) will not be considered. This approach of applying buffer period is consistent with prior analyses conducted in Nordic and other

PRODUCT: V501/V503	PROTOCOL/AMENDMENT VERSION NO.: V503-088-01-v1
REVOPS ID NO: NIS009722	CORE DRC APPROVAL DATE: 18JUL2024
EPIDEMIOLOGY NO.(PE STUDIES ONLY): EP08039.017	

regions to assess vaccine effectiveness in relation to diseases with long latency and/or diagnostic delay [19] [20].

When the outcome of a study is rare, which is the case for RRP, the OR approximates the risk ratio (or relative risk, RR) [42]. Further, incidence density sampling (i.e. random sampling of controls from the available population still at-risk at the particular point in time of the case's diagnosis) also ensures that ORs are a direct estimate of the hazard ratio, again interpretable as the risk ratio in our study [43]. ORs obtained through the conditional logistic regression model will therefore be interpreted as the corresponding RR.

To further increase specificity, the primary analysis will be restricted to AoRRP cases identified using ICD-10 code D14.1 along with appropriate topography/morphology or SNOMED/Norpat codes when available and complete and deemed necessary by experts.

Primary Objective(s): Calculation of Epidemiological Measure(s) of Interest

Descriptive statistics will be calculated for the cases and controls in terms of age, education level (subject/mother), and income (individual/family) using t-test or chi-2-test for differences in continuous and categorical variables, as appropriate. Conditional logistic regression will be conducted for estimation of ORs and corresponding 95% confidence intervals, with adjustment for relevant covariates. For a detailed discussion of covariates of interest, please see Annex 1, which lists subject matter expertise analysis of the association of interest, and potential confounding thereto. Annex 1 also motivates closely the inclusion of covariates described here below.

In case-control studies, it is the odds of exposure which is typically assessed among cases of a disease and then compared with odds of exposure among controls. However, the odds ratio is the same regardless of how it is defined in terms of marginal probabilities, i.e., probability of exposure given disease or probability of disease given exposure are statistically and technically equivalent. As per standard practice, it was therefore chosen to express ORs as the probability of disease given exposure, to provide a measure of the association between vaccine receipt and disease outcome.

Potential confounders such as highest level of family income and highest level of education achieved by the mother and/or subject income/education (tentatively in tertiles relative to the general age-matched population of the respective countries) will be adjusted for when investigating the primary objective, through inclusion in the conditional logistic regression. Given that most young adult females in their late teens/early 20s in Nordic countries have a similar level of education (i.e., almost all complete high school) and income is often limited due to being in school, adjustment for individual-level income and education will be considered and the decision of which variables to include in the model will depend on association of these variables with RRP outcome, and consideration of collinearity. Additionally, confounder assessment based on G-estimation may be undertaken if considered appropriate following discussion between the Sponsor and investigators.

Sensitivity analyses will be conducted in relation to the primary objective to assess the impact of: vaccine exposure definition (fully vaccinated versus ≥1 vaccine dose), age at

PRODUCT: V501/V503	PROTOCOL/AMENDMENT VERSION NO.: V503-088-01-v1
REVOPS ID NO: NIS009722	CORE DRC APPROVAL DATE: 18JUL2024
EPIDEMIOLOGY NO.(PE STUDIES ONLY): EP08039.017	

vaccination (any age and ≥17 years), applying buffer period between vaccination and disease onset of 6 months (from last dose), outcome definition (ICD-10 code D14.1 only versus cases [of D14.1] that have appropriate topography/morphology or SNOMED/Norpat codes, and cases [of D14.1] with at least one associated treatment/procedural code and/or specified with subcode D14.1.A/"larynx papilloma"), restricted to Gardasil use only (as exposure), and personal history of EGW (yes versus no). OR estimates from the regression model will be inspected in terms of point estimates and precision, for comparison with results from the main analysis. Effect size (OR) estimates are expected to vary across most sensitivity analyses. For example, effectiveness may be higher among females that are fully vaccinated, vaccinated at younger age (prior to sexual debut), without history of EGW, and in analyses including a buffer period and more restrictive outcome definition. For transparency, all preplanned analyses are described here.

There will be no adjustment for multiple comparisons in this study. Analyses have been prespecified, discriminating between primary and sensitivity analyses, and all results will be reported.

Secondary Objective: Calculation of Epidemiological Measure(s) of Interest

Annual age-standardized incidence rates (ASIRs) of JoRRP and AoRRP will be calculated, stratified by age group, gender, and calendar period and the p-values from the test for calendar year trends for these rates will be estimated. New cases of JoRRP or AoRRP will be the numerator for the calculation of incidence rates. The denominator will be the accumulated person-time in each calendar year for which the data are analyzed. As this is a highly robust measure over time and the entire population is sampled, it may not be necessary to include confidence intervals; however, given the small number of cases per calendar year, confidence intervals will be calculated.

Overall incidence rates will be adjusted for age according to European Standard Population, because of the larger proportion of older age groups in Nordic countries compared to the World Standard Population.

Exploratory Objective: Calculation of Epidemiological Measure(s) of Interest (e.g., hazard ratios, incidence rates, test/retest reliability)

Risk factors for AoRRP will be explored in the VE analysis conditional logistic regression model to evaluate if they are independently statistically significantly associated with the outcome of RRP, with all other factors held constant. Specifically, vaccination exposure will be at the reference level, i.e., the analysis of risk factor status will effectively be restricted to non-vaccinated individuals.

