Controls: For each case of AoRRP, 10 control subjects free of this diagnosis, at the time of the case's diagnosis, will be identified from the respective countries where cases were diagnosed. As the number of controls per case increases beyond 4, improvement in statistical power diminishes [30]. However, given that data for additional controls are readily available in this database study, 10 controls per case will be selected. Cases and controls will be matched on age (+/- 1 year) at diagnosis, calendar year, and the region where case was diagnosed. By design of the study (nested case-control), cases and controls will also be matched according to length of follow-up in the registries. Controls will be selected from the population at risk at the point in time when a case is diagnosed with RRP. All controls who met the matching criteria will be assigned a random number using SAS statistical software (SAS Institute Inc, Cary, NC) procedures. Then, 10 controls for each case will be selected at random from the pool of eligible controls. Controls will be assigned the same index date as the case to which they are matched. Figure 2 provides an example of case/control subject selection nested within population-based cohort (2006-2021) in this study.

PRODUCT: V501/V503	PROTOCOL/AMENDMENT VERSION NO.: V503-088-01-v1
REVOPS ID NO: NIS009722	CORE DRC APPROVAL DATE: 18JUL2024
EPIDEMIOLOGY NO.(PE STUDIES ONLY): EP08039.017	

Figure 2 Example of case/control subject selection nested within population-based cohort (2006-2021) in this study. Subject 1 is classified as a case without exposure to Gardasil prior to the index (diagnosis) date, and subject 2 is an eligible matched control with exposure to Gardasil prior to the index date.

Exposure assessment: The exposure of interest is GARDASIL or GARDASIL 9 vaccination prior to the index date for each case and matched controls. GARDASIL is a quadrivalent vaccine that is effective against HPV types 6/11/16/18, while GARDASIL 9 is a nonavalent vaccine that is effective against HPV types 6/11/16/18/31/33/45/52/58.

Exposure will be defined in 2 ways:

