- 1. Exposure in primary objective: Fully vaccinated with Gardasil (yes/no) before the age of 17 years. A female will be classified as exposed if she received 3 doses of Gardasil (administered at recommended intervals of 0, 2, and 6 months) or 2 doses if <15 years of age (administered at recommended interval of 0 and 6-12 months). For a 3-dose schedule, the minimum intervals are 4 weeks between dose 1 and dose 2 and 12 weeks between dose 2 and dose 3. For a 2-dose schedule, the minimum interval is 5 months between doses. A female will be classified as unexposed if she did not receive even a single dose of Gardasil prior to being selected as a case or control in the study.
- 2. Exposure in sensitivity analysis: Gardasil vaccination (yes/no). A female who received at least one dose of Gardasil prior to the index date will be classified as exposed.

PRODUCT: V501/V503	PROTOCOL/AMENDMENT VERSION NO.: V503-088-01-v1
REVOPS ID NO: NIS009722	CORE DRC APPROVAL DATE: 18JUL2024
EPIDEMIOLOGY NO.(PE STUDIES ONLY): EP08039.017	

The vaccine registries in Sweden, Denmark, and Norway accurately capture vaccination [31], greatly reducing the risk of exposure misclassification and providing the foundation for a robust observational study. Prior studies relying on Nordic registries for measurement of Gardasil exposure (in relation to risk of anogenital diseases, including cervical cancer) have been conducted successfully in recent years [21] [32].

Secondary Objectives: Ecological Study

Design: Descriptive/ecologic study using nationwide registry data to assess annual agestandardized incidence rates of JoRRP (0-14 years) and AoRRP (15-29 years) by gender.

Cohort: Male and female residents of Sweden, Denmark, and Norway (ages 0-29 years), during the following periods (Table 1):

- Sweden: 2000 2021 (birth cohort, 1971 2021)
- Denmark: 1997 2022 (birth cohort, 1968 2022)
- Norway: 2008 2022 (birth cohort, 1979 2022)

Cases: RRP cases will be identified from national registries using the case definitions for the participating countries as described above.

Exposure assessment: There is no exposure for ecologic study (secondary objective).

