- 1. Separate tables will be prepared with outcome defined using: a) subcode D14.1.A, and b) code D14.1 and/or subcode D14.1A with at least one appropriate procedural code, i.e. DQB10 (Endoscopic extirpation), UDQ25 (Microlaryngoscopy with biopsy), and/or UDQ22 (Microlaryngoscopy).
- 2. Separate tables will be prepared considering: a) age at vaccination (≥17 years vs. any age at vaccination) and b) own history of external genital warts (yes/no).
- 3. Separate tables will be prepared with exposure defined as receiving at least one dose of Gardasil vaccine.
- 4. Separate tables will be prepared applying buffer period between vaccination and disease of 6 months (from last dose).
- 5. Separate tables will be prepared focusing on Gardasil use only as exposure.

¹ All study participants who acquired a first diagnosis of AoRRP as defined for each country.

² 10 controls matched on attained age, region of diagnosis and calendar year of case's diagnosis.

³ Adjustment factors considered for inclusion include education level, income level, country of birth, own history of external genital warts (EGW), and maternal history of EGW.

⁴ A female who received 3 doses (or 2 doses administered at 0 and 6-12 months if <15 years of age) of GARDASIL or GARDASIL 9 before age 17 will be classified as exposed and those who did not receive any dose will be considered unexposed.

PRODUCT: V501/V503	PROTOCOL/AMENDMENT VERSION NO.: V503-088-01-v1
REVOPS ID NO: NIS009722	CORE DRC APPROVAL DATE: 18JUL2024
EPIDEMIOLOGY NO.(PE STUDIES ONLY): EP08039.017	

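### The 6-month buffer analysis is worded to exclude recently vaccinated cases only; controls carry no matching lag, which biases the odds ratio slightly in the vaccine's favour

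*Protocol*

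**What the plan says.** Section 7.11 (Primary Objective) gives the purpose of the buffer as dealing with disease that was present but undiagnosed at vaccination. It says that "a buffer period of 6 months will be applied in sensitivity analyses", and then how: "where cases occurring among individuals within this time period (from last vaccination dose) will not be considered". The list of sensitivity analyses later in Section 7.11 and the notes on Table 5 in Annex 2 repeat the buffer as a 6-month gap between vaccination and disease, counted from the last dose. Controls have no disease date, so neither statement reaches them.

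The rule that does reach controls is in Section 7.1: "The exposure of interest is GARDASIL or GARDASIL 9 vaccination prior to the index date for each case and matched controls". It has no lag. The primary exposure is "Fully vaccinated with Gardasil (yes/no) before the age of 17 years". The same section also says: "Controls will be assigned the same index date as the case to which they are matched". A time since last dose can therefore be computed for every control.

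Section 7.11 expects in advance that effectiveness may be higher "in analyses including a buffer period and more restrictive outcome definition".

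**The concern.** Section 7.11 relies on incidence density sampling to read the odds ratio as a hazard ratio. That holds only if the controls represent the person-time from which an eligible case could arise. A buffer that makes the first 6 months after the last dose ineligible for cases must also take that time out of the controls. As worded, it removes exposed cases from the window and leaves the window's person-time among exposed controls.

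Conditional logistic regression does not repair this. When a case is excluded, her own matched set goes, but recently vaccinated controls in all other sets remain. In a model with exposure alone, deleting sets whose case is vaccinated can only raise the odds ratio (unvaccinated versus vaccinated) or leave it unchanged. The opposing term, removal of recently vaccinated controls, is missing. The analysis then cannot move against the main result, and its one possible direction is the one the protocol says it expects.

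**Working it through.** The protocol states no figure for the size of this effect, so there is nothing to reproduce. The check is algebra plus simulation.

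**Inputs from the protocol.** Buffer of 6 months, or 0.5 years (Section 7.11); primary exposure complete before 17 (7.1); index ages 15 to 29, taken as exact ages 15 to 30 (7.1); 10 controls per case (7.1); odds ratio 3.0, coverage 25% and 60 cases (7.8).

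**Assumed, because the protocol does not give it.** The distributions of age at last dose and of index age, varied below and taken as uniform.

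**Algebra.** Let a₁, a₀ be vaccinated and unvaccinated cases, and b₁, b₀ the same for controls. The odds ratio (unvaccinated versus vaccinated) is (a₀ × b₁)/(a₁ × b₀). Let f be the share of exposed persons in the window, with equal hazard inside and outside it.

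- Case-only rule: a₁ becomes a₁(1−f), so the odds ratio is multiplied by 1/(1−f).
- Same rule for both groups: b₁ also becomes b₁(1−f), and the factors cancel.

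**f for last dose at 12–17 and index age 15–30.** In the window: 2/5 × 0.5/15 + 1/10 × 0.25/15 = 0.0150. Vaccinated by the index date: 3/5 + 2/5 × (1 − 1/15) = 0.9733. So f = 0.0150/0.9733 = 1.5%.

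The other rows follow in the same way:
- Last dose 15–17, index 15–30: (0.5/15)/(1 − 1/15) = 3.6%.
- Last dose 12–17, index 15–20: 0.045/0.92 = 4.9%.
- Last dose 15–17, index 15–20: 0.1/0.8 = 12.5%.

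**Simulation.** 400,000 age-matched sets (1:10, 25% coverage), conditional maximum likelihood, equal protection inside and outside the window:

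| Last dose | Index age | f | 1/(1−f) | True OR 1: case-only / both groups | True OR 3: case-only / both groups |
|---|---|---|---|---|---|
| 12–17 | 15–30 | 1.5% | 1.016 | 1.015 / 0.999 | 3.07 / 3.02 |
| 15–17 | 15–30 | 3.6% | 1.037 | 1.042 / 1.000 | 3.12 / 3.01 |
| 12–17 | 15–20 | 4.9% | 1.051 | 1.054 / 1.001 | 3.18 / 3.03 |
| 15–17 | 15–20 | 12.5% | 1.143 | 1.166 / 1.008 | 3.42 / 3.00 |

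With last dose spread over 10–17 and index ages 15–29, f is about 1.2%, a factor of 1.012. Over the full age range the factor is therefore about 1.012 to 1.037: 3.0 becomes 3.0 × 1.012 = 3.04 to 3.0 × 1.037 = 3.11. Vaccine effectiveness moves from 1 − 1/3.0 = 66.7% to between 1 − 1/3.04 = 67.1% and 1 − 1/3.11 = 67.8%.

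**Where it acts.** Primary exposure ends before 17, so the effect is zero for index ages of about 17.5 and over.

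**Expected count.** With 60 cases, 25% coverage and odds ratio 3, the exposed share of cases is (0.25/3)/(0.25/3 + 0.75) = 0.10, or 6 cases. The buffer would drop 6 × 0.015 = 0.09 to 6 × 0.036 = 0.21 of a case on average.

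**The situation the buffer is meant for.** If there is no protection inside the window, the first scenario with true odds ratio 3 gives 2.94 without a buffer, 3.07 with the case-only rule and 3.02 with the rule applied to both groups. The buffer is worth having; its case-only form overshoots.

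**The case against.** The strongest reply is that the protocol nowhere says that recently vaccinated controls stay exposed in the buffered analysis. This is inferred from a rule that names cases and a general exposure rule without a lag. Section 7.10 shows that an SAP is expected, and the SAP could apply the buffer to both groups. This stands as a caution about how the analysis will be run. It does not clear the wording: the protocol states a rule, Section 7.11 says that all preplanned analyses are described there, and a programmer following the text would code the case-only version.

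The reply is also right on size. The protocol places routine vaccination at about 10 to 12 years and most diagnoses at 20 to 40, so few exposed controls should fall in the window, and uniform index ages probably overstate f. The expectation of higher effectiveness with a buffer also has a legitimate basis, since removing disease already present at vaccination can raise the estimate honestly.

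Two stronger readings do not hold:

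- A reader might infer from the small numbers that the asymmetry could carry a result over the 1.33 bound. With 54 unvaccinated and 6 vaccinated cases against 450 and 150 controls, the odds ratio is 3.0 (Woolf lower bound 1.27). Dropping one vaccinated case gives 3.6 (1.41). A rule applied to both groups drops the same case and about 2 of the 150 exposed controls (150 × 0.012 = 1.8): 54 × 148/(5 × 450) = 3.55 (1.39). Almost all of the move is the fragility of six exposed cases; the asymmetry accounts for about 0.05.
- A reader might carry the calculation over to vaccination at 17 or later, where the window share is larger. Section 7.11 and the Table 5 notes list the buffer and age at vaccination as separate analyses and do not cross them.

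**Conclusion.** Wrong as written, and minor. Taken literally, the buffer rule excludes cases within 6 months of the last dose and leaves controls in the same position exposed, so the odds ratio (unvaccinated versus vaccinated) is biased upward by about 1/(1−f). The direction follows from the wording. The size rests on assumed age distributions: about 1 to 4% for vaccination before 17 over index ages 15 to 29, and about 5 to 15% only if index dates cluster at 15 to 20. With about 60 cases this is small beside the sampling error. A reader might infer that the primary result is compromised. The documents do not support that, because the buffer belongs to a sensitivity analysis and the success criterion concerns the unbuffered primary comparison.

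**What to change.** State in Section 7.11, and repeat in the Table 5 notes of Annex 2, that the 6-month rule applies identically to cases and controls at the shared index date. Either of two forms would do: exclude from the buffered analysis any woman, case or control, whose last dose was less than 6 months before her index date; or, in both groups, count exposure only from 6 months after the last dose. In the simulations both forms returned the true odds ratio to within about 1%. The change is one clause in each place. It needs no new data, because controls already carry an index date and vaccination dates, and under the exclusion form it costs a few controls.
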